## Trial registration

ClinicalTrials.gov: NCT04613362

## Trial registration: data set

## Protocol version September 30, 2022

## Funding

Veterans Health Administration VA Health Services Research and Development  
HSRD IRP 20-002

## Roles and responsibilities: sponsor contact information

## Roles and responsibilities: sponsor and funder

## Roles and responsibilities: committees

# Introduction

## Background and Rationale

1. Description of research question and justification for undertaking the trial, including summary of relevant studies (published and unpublished) examining benefits and harms for each intervention

Individuals with chronic migraine routinely face barriers that limit their access to evidence-based (EB) behavioral headache treatment. With the Veterans Health Administration (VHA) infrastructure dedicated to efficient telehealth delivery into patient homes, the delivery of a behavioral intervention for headache (HA) via the telehealth platform is primed to address barriers of in-person care delivery and holds considerable promise to reach and reduce Veteran patients' headache days.

An evidence base of over 300 studies addressing behavioral headache interventions has exerted a substantive influence on contemporary headache pain management. (Rains, Penzien, McCrory, & Gray, 2005) Behavioral treatments have consistently been shown to be significantly more effective than control conditions and yield clinically-meaningful benefit, (Campbell & Penzien, 2000) and have been found to be similarly efficacious to preventive pharmacotherapy, (Holroyd et al., 2001; Holroyd & Penzien, 1990; Powers et al., 2013) leading numerous professional practice organizations to recommend behavioral headache treatments as front-line interventions for chronic migraine (CM). For example, drawing upon evidence from an Agency for Healthcare Research and Quality (AHRQ)-funded meta-analysis (Goslin et al., 1999), the U.S. Headache Consortium, a multidisciplinary assemblage of seven professional organizations including the American Headache Society, (Silberstein & Consortium, 2000) recommended use of cognitive behavioral therapy (CBT) for CM. (Campbell & Penzien, 2000) Thus, the efficacy and value of behavioral headache interventions has been unequivocally demonstrated—their effect sizes are comparable to pharmacotherapy, the observed improvements are durable, they are essentially free of adverse events, and their use is strongly endorsed by multiple headache medicine stakeholders.

Despite strong empirical support and endorsement by professional practice organizations, behavioral interventions are not widely available to headache patients. (Penzien, Irby, Smitherman, Rains, & Houle, 2015) Even when trained practitioners are available, clinic-based behavioral treatments remain inaccessible to many, given time restraints for patients. Considerable effort has been devoted to making behavioral headache therapies more accessible through development of limited therapist-contact formats (3-5 clinic appointments). Self-management skills are introduced in clinic by a therapist, whereas skills-training occurs at home. This research suggests behavioral self-management interventions for headache can prove highly beneficial if delivered in a compelling format designed to enhance patients' sustained engagement, thereby reducing treatment attrition. Despite the burgeoning empirical evidence that a broad variety of interventions are efficiently and effectively delivered via telemedicine approaches, this strategy has not yet been empirically studied for headache pain management. Therefore, we aim to implement and test a telemedicine-based delivery of CBT for CM employing our manualized migraine treatment protocol.

## Background and rationale: choice of comparators

TENACITY's manualized CBT sessions are adaptable through the delivery medium (telehealth vs in person), by number of sessions, and by the clinical role of the interventionists. The EHUT comparator was chosen to allow each site the flexibility of delivering an appropriate behavioral therapy (Grinberg et al., 2023) alternative.

## Objectives

The objective of this study is to conduct a pilot randomized controlled trial (RCT) and determine the feasibility of the implementation of a cognitive behavioral therapy (CBT-HA) protocol for headache delivered via telemedicine (TENACITY) compared to enhanced headache usual treatment (EHUT).

The investigators will recruit Veterans diagnosed with chronic migraine during the one-year recruitment period across the 3 VAMCs. The investigators will randomize eligible Veterans to participate either in the TENACITY intervention (n=50) or treatment as usual (n=50).

The specific aims are threefold:

Aim 1: To develop a bundle of evidence-based practice (EBP) implementation strategies to engage 3 VA Medical Centers [2 Headache Centers of Excellence HCoEs and 1 general neurology service] and facilitate their local adaptation and implementation of Cognitive Behavioral Therapy (CBT) (TENACITY) through the vehicle of telehealth services.

Aim 2. To conduct a pilot RCT and determine the preliminary efficacy and feasibility of TENACITY compared to TAU across 3 VA sites. We will conduct a superiority analysis.

Hypothesis 2: Veterans receiving TENACITY will experience a statistically significant reduction in routine clinical headache metrics: headache frequency [headache days per month] (primary outcome), headache-related impairment and psychological symptoms (secondary outcomes) compared to enhanced headache usual treatment at 3 and 6 months.

Aim 3: The investigators will conduct exploratory cost analysis of TENACITY from the Veteran's perspective, using inputs from the pilot RCT, and a two-year budget impact analysis from the VHA's perspective, incorporating the costs of implementation as well as direct costs (and cost-savings,) of providing the TENACITY intervention over all HCoEs to VHA.

Hypothesis 3: TENACITY will be cost-effective and provide value to Veterans and VHA.

## Trial Design

TENACITY is a single-blind, randomized, controlled, pilot trial with a single intervention arm and an enhanced headache usual treatment (EHUT) control arm analyzed as intention-to-treat. This multi-site study has a 31-day run-in/screening period to confirm chronic migraine and an approximately 12-week treatment period. Follow-up assessments are conducted at 3 and 6 months post-treatment initiation.

## Methods: Participants, interventions, and outcomes

### Study Setting

Participants will be recruited from three geographically distinct VA medical centers. Site one hosts a large, multidisciplinary HCoE, and is neurology-led with a strong health psychology program. Site two hosts a smaller VA Headache Consortium Center, is neurology-led, and has a developing health psychology program. Site three has no established HCoE and is a large-volume site with no health psychology program for headache.

All study procedures will be conducted via telehealth, with no in-person, face-to-face communication.

### Eligibility Criteria

*Inclusion criteria.* Veteran participants within the VHA medical system with an ICD-10 diagnosis of chronic migraine who complete at least 28 days of headache diary at baseline with a confirmed frequency of  $\geq 8$  headache days per month at baseline are eligible for this study.

*Exclusion criteria.* Veteran patients with any of the following diagnoses are ineligible for this study: post-traumatic headache, cluster headache, other primary headache, post-whiplash headache, and trigeminal autonomic cephalalgia diagnosis. Also excluded are participants who have received  $\geq 90$  days opioid therapy from the date of chart screening; have a current diagnosis of severe cognitive impairment indicated by Short Portable Mental Status Questionnaire (SPMSQ); have a diagnosis of traumatic brain injury  $\leq 1$  year before diagnosis of chronic migraine or worsening of chronic migraine as indicated by post-traumatic headache screening tool; suffer from a disabling psychiatric illness (as noted by clinician); have had a psychiatric hospitalization in the last 6 months; relate daily suicidal ideation within the last 2 weeks as indicated by the PHQ-9 with an answer of "3" to question nine; have severe depression, as indicated by PHQ-9 score  $\geq 20$ ; are terminally ill (life expectancy of  $<12$  months as noted by clinician); decline to or cannot use the Annie App; have been treated by a HCoE clinical health psychologist in last two years.

*Interventionists:* Two clinical psychologists employed by 2 of the 3 VAMCs trained to deliver CBT for Headache manualized behavioral treatment will provide the intervention. One of the psychologists will provide a telehealth clinic to the third site (VAMC) which is without any clinical psychologist trained in CBT-HA in addition to the local site. The two psychologists met to coordinate the treatment protocol prior to the start of the intervention.

### Interventions: description

The TENACITY intervention consists of protocolled, manualized, short-term cognitive behavioral therapy for headache (CBT-HA) sessions which are administered via a telehealth delivery platform. Each session is approximately 50 minutes and follows a similar structure: (1) agenda setting (2) home practice check-in (3) learning a new skill (4) goal setting for home practice. The treatment will be delivered over approximately six biweekly sessions. (Grinberg et al., 2023)

The enhanced headache usual treatment (EHUT) intervention consists of a referral to behavioral pain therapy contingent on the specific site. The therapies available are cognitive behavioral therapy for chronic pain (CBT-CP), integrated pain mindfulness, and dialectical behavioral therapy. Depending on which format is offered at the specific site, these therapies will be delivered either individually or in a telehealth group setting.

Interventions will be initiated after patient randomization and subsequent scheduling with the appropriate clinician using the VHA clinical scheduler. Treatment will be administered using the VA telehealth platform, VA Video Connect (VVC) and/or telephone in one to one clinical visits.

### Interventions: modifications

- i. Criteria for discontinuing or modifying allocated interventions for a given trial participant (eg, drug dose change in response to harms, participant request, or improving / worsening disease)

Treatment length and content is able to be modified and adjusted based on clinician discretion and mutual agreement with the participants.

### Interventions: adherence

- i. Strategies to improve adherence to intervention protocols, and any procedures for monitoring adherence (eg, drug tablet return; laboratory tests)

Clinicians have the option of scheduling participants for subsequent sessions ahead of time to potentially improve adherence. Post-hoc chart abstractions will be conducted to assess intervention adherence.

### Interventions: concomitant care

- i. Relevant concomitant care and interventions that are permitted or prohibited during the trial

There is no prohibited concomitant care during the course of the study. Participants will be asked to continue their usual medical headache care.

### Outcomes

[figure not shown]
The primary outcome to be evaluated is change in the number of self-reported headache days during the past 31 days at 3 months compared to baseline. This outcome is considered the gold standard for prospective migraine research.

Secondary outcomes include the change in headache-related impairment and psychological symptoms at 3 and 6 months compared to baseline. These include a battery of well-validated health questionnaires of functioning and symptoms that are tracked as part of routine headache care services both in VA and non-VA healthcare systems and include the following: Migraine-Specific Quality of Life Questionnaire (MSQ); MIDAS; Headache-specific Pain Catastrophizing Scale (HPCS); Headache Management Self-Efficacy Scale (HMSE); Post Traumatic Stress Disorder (PCI-5); PHQ-9; GAD-7; Veterans RAND VR-12; Insomnia Severity Index (ISI).

## Participant timeline

- i. Time schedule of enrolment, interventions (including any run-ins and washouts), assessments, and visits for participants. A schematic diagram is highly recommended (see Figure)

Upon enrollment, participants will begin a run-in period of a 31-day electronic headache diary. Participants will be asked to participate in a baseline interview and to complete health questionnaires. On completion of baseline headache diary, if all inclusion criteria are met, participants will be randomized to either CBT-HA (TENACITY) or EHUT. Consults will be placed to the appropriate clinical providers, with clinics contacting participants to schedule treatment. Participants will complete the 31-day headache diary and health questionnaires again at approximately 3 and 6 months after treatment initiation, along with an additional treatment satisfaction survey.

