## Blinding (masking)

A TENACITY protocol evaluation will be conducted with participants at approximately 3 months post-treatment initiation in order to evaluate the study arms and exercises used in treatment. To protect research personnel blindness, the research staff member who is responsible for randomization will be the sole staff member to conduct these evaluations and collect self-reported medical care received during the prior 3 months.

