## Methods: Data collection, management, and analysis

### Data collection plan

- i. Plans for assessment and collection of outcome, baseline, and other trial data, including any related processes to promote data quality (eg, duplicate measurements, training of assessors) and a description of study instruments (eg, questionnaires, laboratory tests) along with their reliability and validity, if known. Reference to where data collection forms can be found, if not in the protocol

Participants will complete a baseline interview and health questionnaires via phone or electronically using VA Qualtrics. They will be assigned a 31-day headache diary using VA Annie app. Research staff will obtain Veteran permission to audio-record the interviews. Each interview will be recorded and transcribed. The health questionnaires and headache diary will also be completed at 3-month and 6-month post-treatment initiation, along with a treatment satisfaction survey.

At the end of the 31-day run-in period, the participants will be contacted by phone to review the headache diary. If the participant self-reported  $\geq 8$  headache days over the course of the prior 31 days and completed the first question of the headache diary on at least 28 days, s/he will remain eligible for the study. If the participant did not meet these criteria, they will be invited to complete an additional 31 days of headache diary, with the same stipulations applied. If they choose not to complete the headache diary a second time, they will be considered ineligible, removed from the study and sent back to the HCoE clinical provider to review other treatment options. Participants enrolled in the study will then be randomized to either the TENACITY arm or the EHUT control arm of the study.

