## Primary Outcomes Collection

Reduction of headache days in the 31 days prior to the 3-month post-start of treatment mark is the primary outcome; reduction in headache days in the 30 days prior to the 6-month post-start of treatment mark will allow for measurement of cumulative benefit and persistence of efficacy.

The VA Annie mobile application (Saleem et al., 2020) will be utilized as the platform for a daily headache diary. A protocol has been designed (Table 1) to send daily automated text messages to each participant for a total of 31 consecutive days. Participant responses are stored in the Annie system and are accessible by study staff. If a participant responds that they had a headache, eight additional questions are asked as indicated in Table 1. After being prompted with an Annie question, if the participant does not respond, a reminder message is sent every twenty minutes, with a maximum of three reminders per question.

Q	Text	Response Options	Action
1	Hello, it's Annie. Did you have a headache today?	Yes – HA 2 No – HA 1	If HA 2 → Q2 If HA 1 → Q9
2	On a scale from 0-10, with 0=none and 10=worst, how severe was the headache?	PN 0 – PN 10	If response → Q3
3	Was the pain worse on one side of your head?	Yes – SD 2 No – SD 1	If response → Q4
4	Was the pain pounding/throbbing?	Yes – PD 2 No – PD 1	If response → Q5
5	Did light bother you?	Yes – LT 2 No – LT 1	If response → Q6
6	Did sound bother you?	Yes – SO 2 No – SO 1	If response → Q7
7	Did you feel nauseated or sick to your stomach or vomit?	Yes – VO 2 No – VO 1	If response → Q8
8	Was the pain made worse with routine activities such as walking or climbing stairs?	Yes – MV 2 No – MV 1	If response → Q9
9	On a scale from 0-10, with 0=none and 10=worst, how much did the headache interfere with your life today?	IN 0 – IN 10	

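### Follow-up is dated from treatment start, with no exact dating event and no substitute date for a randomised Veteran who never starts

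*Combined protocol and SAP*

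**What the plan says.** Five sections give follow-up an anchor, and all five use treatment start:

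- Participant timeline: "Participants will complete the 31-day headache diary and health questionnaires again at approximately 3 and 6 months after treatment initiation".
- Trial Design: "Follow-up assessments are conducted at 3 and 6 months post-treatment initiation".
- Data collection plan: "The health questionnaires and headache diary will also be completed at 3-month and 6-month post-treatment initiation".
- Primary Outcomes Collection, which sets the primary window: "Reduction of headache days in the 31 days prior to the 3-month post-start of treatment mark is the primary outcome".
- Blinding (masking), for the treatment evaluation: "A TENACITY protocol evaluation will be conducted with participants at approximately 3 months post-treatment initiation".

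Other sections give a time with no anchor. Objectives has "compared to enhanced headache usual treatment at 3 and 6 months", Outcomes has "change in the number of self-reported headache days during the past 31 days at 3 months compared to baseline", and the model in Statistics: outcomes contrasts Month 3 with Baseline. No section counts follow-up from randomisation.

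Interventions: description places initiation after randomisation and scheduling. Participant timeline and Allocation: implementation describe the steps between: consults go to the clinics, and the clinics or schedulers then contact the Veteran. No limit is set on how long this may take.

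Trial Design describes an "control arm analyzed as intention-to-treat", and Statistics: outcomes repeats the intention-to-treat commitment.

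**The concern.** The primary outcome comes from a daily app diary that must be switched on about two months after time zero. If time zero is an event after randomisation that may not happen, the timing rule can itself determine who has a month-3 outcome. Those who do would be a group formed after randomisation, and the protection that randomisation gives to the comparison would be weakened. Staff would also have to decide case by case whether and when to send a diary to a non-starter.

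Waits may also differ between arms, because the arms use different services. Two psychologists deliver TENACITY across three sites (Eligibility Criteria, Interventionists). EHUT is whatever behavioural pain therapy the site offers, individually or in a group (Interventions: description). Unequal waits would place the two arms' diaries at different distances from baseline. Nothing in the documents shows that waits do differ, and nothing makes them equal.

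**Working it through.** The plan gives no figure on this point to reproduce, so the check is of the text, followed by illustrations under stated assumptions.

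**1. Is there any other anchor?** The five anchored sections all use treatment start. The unanchored ones (Objectives, Outcomes, Statistics: outcomes) supply no alternative date. A figure under Outcomes is not shown and could carry timing detail; the running text does not.

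**2. When is the diary due?** Take 3 months as 91 days (assumption). A 31-day window ending on day 91 begins on day 91 − 31 + 1 = 61. For a Veteran who starts *s* days after randomisation, it covers days *s* + 61 to *s* + 91:

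| Assumed wait *s* (days) | Diary window, days from randomisation |
|---|---|
| 0 | 61–91 |
| 28 | 89–119 |
| 56 | 117–147 |
| never starts | not defined |

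**3. Can the gap be filled later?** The diary is collected prospectively by daily text message (Primary Outcomes Collection). Statistics: analysis population and missing data says that missing data will be evaluated, but names imputation only for Veterans with 28 or more of the 31 diary days. A Veteran with no diary has 0 of 31. Data collection plan: retention offers gift cards and does not say what is collected from those who do not start.

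**4. What does the model do?** The model has arm, visit (Month 3 against Baseline) and their interaction, on days clustered within Veteran. It still fits, and it can keep a non-starter's baseline days. Those days carry no information about that Veteran's month 3.

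**5. How many Veterans?** With 100 randomised (Sample size) and assumed non-start rates:

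- 100 × 0.05 = 5
- 100 × 0.10 = 10
- 100 × 0.20 = 20

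**6. Can a bias be signed?** Let *p* be the share never starting in an arm and *g* the starter-minus-non-starter difference in mean change in headache days (negative means starters improve more). Within an arm, the starter mean minus the all-randomised mean is *p* × *g*. The starters-only contrast (TENACITY minus EHUT) therefore differs from the all-randomised contrast by *p*_T × *g*_T − *p*_E × *g*_E. The inputs below are all assumed:

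- 10% in both arms, *g* = −2 in both: −0.2 + 0.2 = 0 days.
- 10% TENACITY and 30% EHUT, *g* = −1 in both: −0.1 + 0.3 = +0.2 days, against TENACITY.
- 20% in both arms, *g*_T = −4 and *g*_E = −2: −0.8 + 0.4 = −0.4 days, in favour of TENACITY.

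The sign changes with the inputs, and the documents give none of them.

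**The case against.** The best defence has three parts.

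First, start has an ordinary meaning for a therapy made up of sessions, namely the first session, and the figure not shown may say so. That is reasonable, but it settles only the date for those who attend. A Veteran who never attends still has no date.

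Second, counting from treatment start is a legitimate choice, because it puts the diary near the end of a treatment period of about 12 weeks. This stands: the anchor itself is not the error, and the repair can keep it.

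Third, this is a pilot sized by staff resources. That lowers the stakes but does not remove them, since Aim 2 plans a superiority analysis and Hypothesis 2 expects a statistically significant reduction.

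A reader might also infer that the EHUT clock starts at the referral, because Interventions: description defines EHUT as a referral. Selection would then act on TENACITY alone. The documents do not support this. The same section says, without separating the arms, that initiation follows scheduling, and Participant timeline has consults placed before clinics call to schedule. A referral precedes scheduling, so it is not a natural reading of initiation.

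**Conclusion.** The point holds as a gap in the timing rule. A randomised Veteran who never starts has no defined month-3 or month-6 window. Followed as written, the month-3 observations would come from starters, despite the stated intention-to-treat analysis.

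A reader might go further and conclude that the plan excludes non-starters or abandons intention-to-treat. It does neither. No section excludes them, the follow-up text speaks of participants generally, and staff could still send a diary on a date of their choosing. Missing month-3 outcomes are a missing-data problem, not in themselves a departure from analysis by assigned arm. That month-3 data would come from starters is an inference from the absent date.

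The illustrative size is 5 to 20 of 100 Veterans without a defined window, if 5% to 20% never start. No bias in headache days can be stated. Confidence is medium, because start rates and waits are unknown and one figure is not shown. This is a cheap improvement that should be made.

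**What to change.** In Trial Design, Participant timeline, Blinding (masking), Data collection plan and Primary Outcomes Collection:

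1. Define initiation, for assessment timing only, in the same way in both arms (for example, first attended session of the assigned therapy).
2. For any Veteran not started by a fixed interval after randomisation, identical in both arms, date the follow-up windows from that default date.
3. Send the month-3 and month-6 diaries and questionnaires to every randomised Veteran whether or not treatment starts, and analyse by assigned arm.
4. Use the same anchor wording in Objectives and Outcomes.

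The cost is protocol wording and one added rule for triggering the app diary. No treatment changes.

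The downside falls on Veterans who start after the default date. Suppose the default is day 28 and a Veteran starts on day 56. The window stays at days 89–119 from randomisation, which is treatment days 33–63 (89 − 56 and 119 − 56) instead of 61–91. With six sessions at treatment days 0, 14, 28, 42, 56 and 70, 3 are due before that window opens and 5 by its close, against 5 and 6 for a Veteran who starts by the default date. Those who start by then are unaffected.

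A later default affects fewer Veterans but widens the spread from randomisation to the month-3 mark: 91 to 119 days with a 28-day default, 91 to 147 with a 56-day default.

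Reporting time to start and the share never starting, by arm, would be a useful optional addition.
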